2.2 Primary Endpoints

The main endpoint of the study is the difference in AUC (concentration over time in %) of circulating carotenoids in the plasma triacylglycerol-rich lipoprotein (TRL) fraction between two different protein

sources and control (no protein added). These investigated circulating carotenoids will be lycopene and beta-carotene.

More specifically, the data will be evaluated as follows:

- a) Determination of the AUC, using the trapezoidal method (Excel)
- b) Verifying whether data is normally distributed. If not, log-transformation will be attempted.
- c) Data will be baseline subtracted – conc. at time 0 will be subtracted from all later values. Alternatively, in the frame of a sensitivity analysis, original data will be used (with baseline concentrations as covariate).
- d) Negative concentrations at time points, if occurring, will be treated as “negative area”, i.e. this area will be subtracted from the positive area.
- e) The baseline conc. will be included as a co-variate in the model.

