5.1 Outcome definition

Primary outcomes:

Beta-carotene and lycopene

Beta-carotene and lycopene will be measured in the plasma triacylglycerol rich lipoprotein (TRL) fraction in μM at baseline (0h) and 2h, 3h, 4h, 5h, 6h, 8h, 10h after test meal intake. Using non-compartmental analysis, repeated measures over time of carotenoids will be summarised as postprandial AUC (trapezoidal approach) using the PK functions plug-in for Microsoft Excel and will be validated in a statistical software such as R or SAS system. Of note, it is planned to baseline-subtract all further concentrations (hours 2-10), and to also subtract potentially occurring negative values from the AUC.

Baseline concentrations will be included as co-variates into the linear mixed model.

Secondary outcomes:

Triglycerides

Triglycerides will be measured in the plasma in mg/dL at baseline (0h) and 2h, 3h, 4h, 5h, 6h, 8h, 10h after test meal intake. Using non-compartmental analysis, repeated measures over time of triglycerides will be summarised as postprandial AUC (trapezoidal approach) using the PK functions plug-in for Microsoft Excel and will be validated in a statistical software such as R or SAS system.

Minor abundant carotenoids:

Isomers of beta-carotene and lycopene will be treated as the all-trans native form, i.e. all chromatographic peak area will be combined if isomers are identified in the plasma-TRL fraction.

If alpha-carotene or other carotenoids such as lutein and beta-cryptoxanthin can be measured (if chromatographic sensitivity is sufficient), AUC in the TRL fraction will also be determined, as described for beta-carotene and lycopene.

They will be accounted for in the analyses as secondary outcomes with similar analysis methodology

Total carotenoids will be produced by summing up all carotenoids measured and analysed as the primary endpoint

Carotenoids after colonic digestion:

Native carotenoids after colonic digestion, as well as excreted degradation products such as apo-carotenoids will be investigated, as far as the analytical capabilities allow. As no previous data exists in this respect, this part will be of highly explorative character.

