5.2 Analysis methods

The primary endpoint, AUC of either lycopene or beta carotene will be analysed using a linear mixed model using randomization sequence and treatment (test meal) as fixed terms and patient within sequence as a random term taking into account the cross-over design as described in chapter 5 of "Cross-Over Trials", Senn (2002). Baseline will be included as a co-variate.

Assumptions of normality and equality of variance will be verified by normality plots and boxplots, respectively. If data is non- normally distributed, log transformation will be attempted.

Non-parametrical analysis (Friedman tests followed by Wilcoxon- Mann- Whitney test) may be chosen in case data is not normally distributed, if log-transformation is not successful, though based on earlier studies data normally follows normal distribution.

The secondary endpoints - triglycerides, and if feasible additional carotenoids (see 5.1 above) will be analysed by the same methodology.

A linear mixed model will be first performed for each main outcome, with either baseline corrected AUC of lycopene or beta-carotene as the observed, dependent variable, and randomization sequence, test-meal as the independent variable (fixed factor) and patient within sequence as random factor. Pairwise comparisons of the intervention will be performed by means of Tukey's post-hoc test. Additionally, sensitivity analysis with the original outcomes (lycopene or beta-carotene) as dependent, randomization sequence, test meal and baseline concentration of the outcome as fixed factors and patient within sequence as random factor. 95% confidence intervals will be reported for the main outcomes.

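### The SAP gives two primary models, with and without the baseline covariate; under the one it states most often, the untransformed sensitivity analysis cannot differ from the primary analysis

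*SAP*

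**What the plan says.** **Outcome.** SAP 2.2(c) defines the baseline correction: "conc. at time 0 will be subtracted from all later values". SAP 2.2(d) keeps negative increments rather than setting them to zero: "this area will be subtracted from the positive area". Samples are taken at 0, 2, 3, 4, 5, 6, 8 and 10 h (SAP 2.9 and 5.1), and AUC is trapezoidal.

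**Primary model with baseline.** SAP 2.2(e): "The baseline conc. will be included as a co-variate in the model". SAP 5.1: "Baseline concentrations will be included as co-variates into the linear mixed model". SAP 5.2, first paragraph: "Baseline will be included as a co-variate". Protocol section 11 also lists the baseline carotenoid concentration as a covariate for the baseline-corrected AUC.

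**Primary model without baseline.** The last paragraph of SAP 5.2 sets out the model again, "with either baseline corrected AUC of lycopene or beta-carotene as the observed, dependent variable, and randomization sequence, test-meal as the independent variable (fixed factor", with patient within sequence as the random term. No baseline term appears.

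**Sensitivity analysis.** SAP 2.2(c): "in the frame of a sensitivity analysis, original data will be used (with baseline concentrations as covariate". SAP 5.2, last paragraph: "Additionally, sensitivity analysis with the original outcomes (lycopene or beta-carotene) as dependent", here with baseline among the fixed terms.

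**Fallbacks.** If the data are not normal, SAP 2.2(b) and 5.2 allow a log-transformation, and SAP 5.2 then allows rank tests. Protocol section 11 rules out the log-transformation.

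**The concern.** A sensitivity analysis is meant to show whether the meal effect depends on a debatable choice, here how the 0 h concentration is handled. Subtracting baseline and adjusting for it are two ways of using the same number. If the primary model does both and the sensitivity model only adjusts, the subtraction may simply be absorbed by the covariate. The check would then agree by construction.

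The SAP also does not settle whether the primary model contains the covariate. Two different models can both claim to be prespecified. They can give different meal contrasts and p-values, and the choice between them could be made after the data are seen.

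**Working it through.** **Plan's own figure.** The plan gives no figure for the effect of baseline handling. The nearest is the power in SAP 2.6 (96% with 24 participants, 83% with 18). It reproduces as 96.2% and 83.5% from a noncentral t for paired differences (difference 4, SD 4, two-sided alpha 0.05/6, df = n - 6). It does not depend on the baseline term.

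**Step 1: trapezoid weights.** The intervals are 2, 1, 1, 1, 1, 2 and 2 h. The weights at 0, 2, 3, 4, 5, 6, 8 and 10 h are 1, 1.5, 1, 1, 1, 1.5, 2 and 1, which sum to 10.

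**Step 2: effect of subtraction.** Negative area is netted, so the correction is linear:

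AUC_sub = AUC_raw - 10 × C0.

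If only the later values were corrected and the 0 h point left as measured, the factor would be 10 - 1 = 9. The argument is the same.

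**Step 3: covariate in both models.** Write AUC_raw = sequence + meal + b × C0 + patient + error. Subtracting 10 × C0 from both sides gives AUC_sub = sequence + meal + (b - 10) × C0 + patient + error. The meal and sequence terms, variance components and residuals do not change. Meal contrasts, standard errors, p-values and restricted likelihood must therefore coincide. This holds with patient random (SAP 5.2) or subject fixed (Protocol section 11).

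**Step 4: numerical check.** The documents give no concentrations, so all values are assumed. Crossovers with 24 subjects, the six sequences and the SAP sampling times were simulated, 500 data sets at each of three persistence levels. Persistence is the share of the 0 h concentration still present beneath the meal response at later times. Decisions were taken at the two-sided 0.83% level of SAP 2.6.

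One example, protein 1 versus control:

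| Model | Estimate | SE | p | Baseline slope |
|---|---|---|---|---|
| Subtracted AUC, 0 h covariate | 0.263 | 0.186 | 0.166 | 1.263 |
| Raw AUC, 0 h covariate | 0.263 | 0.186 | 0.166 | 11.263 |
| Subtracted AUC, no covariate | 0.279 | 0.181 | 0.131 | none |

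Data sets with at least one differing decision among the three meal comparisons:

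| Comparison | Persistence 1.0 | 0.85 | 0.7 |
|---|---|---|---|
| Subtracted with covariate vs raw with covariate | 0/500 | 0/500 | 0/500 |
| Subtracted without covariate vs raw with covariate | 28/500 (5.6%) | 34/500 (6.8%) | 72/500 (14.4%) |
| Log subtracted vs log raw, both with covariate (where the log is defined) | 109/500 | 94/474 | 48/167 |
| Subtracted vs raw, both with preliminary-visit sample as covariate | 172/500 | 167/500 | 186/500 |

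In the first row the largest difference over all 1,500 data sets was about 4e-9 in estimates and 2e-8 in p-values, which is numerical noise.

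**Step 5: primary model without the covariate.** Omitting C0 fixes its slope at 0 for subtracted AUC, which is +10 for raw AUC. Whether that costs precision depends on persistence. In 150 further simulated data sets per setting, the mean ratio of standard errors (without covariate to with) was 0.995 at persistence 1.0, 1.01 at 0.85, 1.04 at 0.7 and 1.23 at 0.3. A single separate example gave 0.076077 / 0.060814 = 1.25.

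**The case against.** The strongest counter-argument is that the last paragraph of SAP 5.2 is the only place that sets out both models side by side, and there they differ: the primary has no baseline term and the sensitivity model has one. By the identity in step 2, raw AUC with the covariate is the same as subtracted AUC with the covariate. That paragraph therefore already compares the model without the covariate against the model with it. A robustness check exists, and the defect is contradictory wording about which model is primary. This stands, and it limits the point.

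A reader might infer that the sensitivity analysis will always confirm the primary result. The documents do not support that. Besides the last paragraph of SAP 5.2, a log-transformation breaks the identity, and the rank tests have no covariate to absorb the subtraction. The identity also needs the covariate to be the visit's own 0 h value. SAP 2.2(c) and 5.1 point to that value but do not state it everywhere, and a preliminary-visit sample also exists. Finally, SAP 5.2 speaks of the original outcomes without saying raw AUC, although SAP 2.2(c) contrasts original with baseline-subtracted data.

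A reader might also infer a definite precision loss of about a quarter if the covariate is dropped. That is one end of a simulated range; at full persistence there is no loss.

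Nor do the documents say how agreement would be reported. A redundant secondary run does not by itself bias the primary estimate or change its error rate or power.

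**Conclusion.** The point holds in conditional form. The SAP contains two conflicting primary models. Under the one stated in SAP 2.2(e), 5.1, the first paragraph of 5.2 and Protocol section 11, the planned sensitivity analysis on untransformed AUC returns the same meal contrasts, standard errors and p-values, with only the baseline slope moving by 10. That is algebra and needs no assumed values, but it requires the same-visit 0 h concentration as a linear covariate in both models. Under the model in the last paragraph of SAP 5.2 the sensitivity analysis is informative, but the primary model contradicts the other four statements.

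Under assumed concentrations, the two candidate primary models disagreed on at least one decision in about 6% to 14% of simulated data sets. Omitting the covariate cost between nothing and roughly 20-25% in standard error, depending on baseline persistence. These ranges are illustrative, because the documents give no baseline variance or persistence. The untransformed analysis is the planned path: SAP 5.2 expects normality on the basis of earlier studies. The SAP should be corrected before the data are analysed.

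**What to change.** 1. State one primary model: baseline-subtracted AUC with sequence and test meal as fixed terms, patient within sequence as random, and the same visit's 0 h concentration as covariate. SAP 2.2(e), 5.1, the first paragraph of 5.2 and Protocol section 11 already call for the baseline covariate.
2. Define baseline explicitly as the 0 h sample of that visit, so that the preliminary-visit sample cannot be meant.
3. Rewrite the last paragraph of SAP 5.2 to agree.
4. Replace the sensitivity analysis in SAP 2.2(c) and 5.2 with one that can differ. One option is baseline-subtracted AUC without the covariate. Another is to split baseline into the subject's mean and the within-subject deviation, each with its own slope.

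The cost is SAP wording and one different model run per outcome. No change to data collection or sample size is needed.

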2.3 Secondary Endpoints

Secondary endpoints will include the following:

- a) In addition to carotenoids, triglycerides will be investigated, also as the area-under time curve, though based on plasma samples (not plasma TRL fraction).
- b) Total carotenoids as the sum of individual concentrations of all carotenoids measured in the plasma triacylglycerol-rich lipoprotein (TRL) fraction will also be analysed through the calculation of the AUC
- c) timely appearance of carotenoids in the plasma-TRL fraction, i.e. their kinetics, including e.g. C_{max} , t_{max} .
- d) Another secondary endpoint will be carried out through the collection of complete fecal samples in a small number of subjects – two subjects will be selected based on voluntary availability. The purpose of this pilot sub-trial is to detect potential (colonic) carotenoid degradation products such as apo-carotenoids as well as non-degraded native carotenoids, as more polar metabolites of carotenoids have been associated with health benefits. However, no data on colonic metabolites is available so far [28]. This pilot sub-trial could be used as a later base for a follow-up study, should interesting metabolites be measured at biologically relevant concentration. In addition to the measurements of metabolites, six participants will be selected –also based on voluntary availability- to take an aliquot from their stool in order to characterize the microbiota present within the collected samples by 16S rDNA gene sequencing or similar tools.

2.4 Trial design

This is a post-prandial double blinded, randomized and controlled cross-over study with 3 periods and six sequences.

A 6x3 Williams Crossover design is applied for the six sequences. Equal allocation of six patients per sequence is planned. Patients meeting the inclusion criteria will receive three different interventions (2 different meals with added protein sources and one control meal where no protein is added) at three different time points following a one-week washout period.

A	B	C
B	C	A
C	A	B

C	B	A
A	C	B
B	A	C

Figure 1: 6x3 Williams Crossover Design

2.5 Randomization

A block randomization for six different blocks with a block size of four participants will be performed in R using R-package randomizeBE (version 0.3-4) and function RL4. Randomization will be conducted according to SOP OP-DMS-001 "Randomisation of Studies and un-blinding of data".

[figure not shown]

Figure 2 Schema of test meal sequences for each treatment pattern during the trial phase.

2.6 Sample Size

It is assumed that two different outcomes will be tested as dependent variables and all pairwise comparisons will be performed. First lycopene and then beta-carotene will be tested. This will lead to three statistical tests per carotenoid readout: with the original alpha risk of 0.05 the corrected alpha risk would then be $0.05/6=0.083$ i.e. 0.83%. The Bonferroni adjustment will be used to keep the family-wise error at the specified error level and thus with the total number of pairwise comparisons equal to 6 each pairwise test is at the two-sided 0.83% significance level.

Area under the time – carotenoid concentration is assumed as main outcome for the sample size calculation.

When there are 2 outcomes (lycopene and beta-carotene), 3 treatments and a sample size of 4 in each of the 6 sequences, a 6x3 Williams Crossover inequality test of paired differences will have 96% power to detect a minimum difference of 4% of the area under time curve (AUC) (difference between 20% and 24% of AUC) or greater, assuming that the standard deviation of the paired differences is 4% at the 0.83% significance level. This leads to a total sample size of N=24 participants.

In case of one drop-out per sequence (n=3 per sequence), the power will reduce to 83%, which will still provide sufficient statistical strength. Sample size calculation was performed in nQuery 8 (version 8.3.1.0).

[figure not shown]

Figure 3 Power (%) vs. Sample Size per Sequence; minimum difference = 4%, SD = 4%, significance level = 0.8%

Figure 4 Power (%) vs. Minimum Expected Difference; n per sequence = 4, $SD = 4\%$, significance level = 0.8%

[figure not shown]

Figure 5 Power (%) vs. Standard deviation; $n=4$ per sequence, mean difference = 4%, significance level = 0.8%

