3.1 P- values and multiplicity adjustment

As two statistical tests will be performed per main outcome (beta-carotene and lycopene), the total number of comparisons will be 6 (3 x 2) and therefore multiplicity correction will be applied. A Bonferroni corrected p-value will be used at that level: $\frac{\alpha}{2} = \frac{0.05}{2} = 0.025$. For the three post-hoc tests within each outcome (test meals vs. control), Tukey's post hoc test will be applied.

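### SAP 2.6 misprints the Bonferroni level as 0.083 instead of 0.0083 (power unaffected), and the SAP and protocol give three different rules for the primary comparisons

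*SAP*

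**What the plan says.** SAP 2.6 starts "with the original alpha risk of 0.05", divides by six and writes "the corrected alpha risk would then be $0.05/6=0.083$ i.e. 0.83", the last figure being a percentage. It then says that "with the total number of pairwise comparisons equal to 6 each pairwise test is at the two-sided 0.83% significance level". The power statement uses the same level, "assuming that the standard deviation of the paired differences is 4% at the 0.83% significance level", and the figure captions in that section give 0.8%.

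SAP 3.1, the section on p-values and multiplicity, gives another rule: 0.05/2 = 0.025 for each carotenoid, then Tukey's test for the three pairwise comparisons within it. Its opening count reads "As two statistical tests will be performed per main outcome (beta-carotene and lycopene), the total number of comparisons will be 6 (3 x 2". SAP 5.2 repeats Tukey for the pairwise comparisons and does not mention Bonferroni over six. SAP 2.7 lists three pairwise comparisons for lycopene and three for beta-carotene.

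Protocol section 11 gives a third rule: a repeated measures ANOVA, then Fisher's protected LSD if the F test is significant, with two-tailed p below 0.05 as the criterion. That section has no adjustment for testing two carotenoids.

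**The concern.** A decision threshold should appear once, correctly, and be the same wherever it is used. Here one clause gives two values that differ tenfold, and the larger one is looser than the unadjusted 0.05 it is meant to tighten. Around it, three sections name three procedures for the same six contrasts, and one of them miscounts the tests.

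The stake is the call on a primary contrast with a borderline p-value. If the documents support more than one rule, the choice can be made after the data are seen. The power quoted in SAP 2.6 also belongs to only one of the rules.

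**Working it through.** **1. The corrected level.** 0.05/6 = 0.00833 = 0.83%. The decimal 0.083 is 8.3%, ten times larger. The percentage is right and the decimal is wrong.

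**2. Which level the power calculation used.** Inputs from SAP 2.6:
- difference 4 percentage points, to "detect a minimum difference of 4% of the area under time curve (AUC) (difference between 20% and 24% of AUC) or greater";
- SD of paired differences 4;
- "a sample size of 4 in each of the 6 sequences", so N = 4 × 6 = 24;
- with one drop-out per sequence, N = 3 × 6 = 18;
- two-sided tests.

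The noncentrality is (4/4) × √N, which is 4.899 at N = 24 and 4.243 at N = 18. Power is the probability that a noncentral t variable exceeds the two-sided critical value in absolute size. The SAP does not state the degrees of freedom. I take df = N − 6 (N minus the number of sequences), giving 18 and 12, because this matches both stated powers.

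| Level per contrast | N = 24: critical t, power | N = 18: critical t, power |
|---|---|---|
| Stated in SAP 2.6 | 96% | 83% |
| 0.05/6 | 2.963, 96.2% | 3.153, 83.5% |
| 0.083 | 1.836, 99.8% | 1.891, 98.7% |
| Tukey at 0.025 (step 3) | 2.893, 96.7% | 3.058, 85.6% |

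With the level rounded to 0.0083, the second power is 83.46%, which rounds to the stated 83%. With df = N − 1, 0.05/6 gives 97.0% and 87.7%, and the second does not match. The decimal 0.083 was therefore not used.

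**3. The SAP 3.1 rule on the same scale.** Tukey at 0.025 with three meals rejects when |t| exceeds q(0.975; 3, df)/√2.
- df = 18: 4.091/1.414 = 2.893, a per-contrast two-sided p of 0.0097.
- df = 44 (the within-subject residual with 24 subjects, three periods and a period term): 3.841/1.414 = 2.716, p = 0.0094. Without a period term df is 46 and p is still 0.0094.

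The family-wise bound over the two carotenoids is 0.025 + 0.025 = 0.05.

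**4. The protocol rule.** With three means and the usual ANOVA assumptions, a significant F test followed by LSD holds the error within one carotenoid at 0.05. Across two carotenoids the bound is 0.05 + 0.05 = 0.10.

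**5. The rules side by side at N = 24.**

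| Contrast p | SAP 2.6 (p < 0.0083) | SAP 3.1 (p < 0.0094 to 0.0097) | Protocol section 11 (F test, then p < 0.05) |
|---|---|---|---|
| 0.009 | not significant | significant | significant if F is |
| 0.03 | not significant | not significant | significant if F is |

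**6. The count.** Three meals give three pairs, and 3 × 2 carotenoids = 6, as in SAP 2.6 and 2.7. Two tests per outcome would give 2 × 2 = 4, which contradicts the total in the same sentence of SAP 3.1.

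**The case against.** The case for leaving this as a copy-edit is strong on the decimal. The right figure stands in the same clause, the next sentence says that "each pairwise test is at the two-sided 0.83% significance level", and the power statement agrees. The wrong decimal appears once and is not used again. A corrected level larger than the uncorrected one would puzzle any reader into checking it. All of that stands.

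A reader might nevertheless infer that family-wise error is uncontrolled: six tests at 0.083 have a bound of 6 × 0.083 = 0.498, and 1 − (1 − 0.083)^6 = 0.405 if independent. The documents do not support this. The operative level in SAP 2.6 is 0.83%, with a bound of 6 × 0.00833 = 0.05, and SAP 3.1 does not use 0.083. Nor are the six tests independent, since the three contrasts within a carotenoid share meals. In simulation, even a literal use of 0.083 gave about 0.25 to 0.35, for an assumed correlation between carotenoids of 0.9 down to 0.

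On the competing rules, it can be said that both SAP rules bound the family-wise error at 0.05, that they differ only slightly, and that the 2.6 power is a little conservative for the 3.1 rule. That is correct. It can also be said that the SAP is the governing analysis document, and that the power paragraph in protocol section 13 foresees adjusting individual contrasts for multiplicity. But SAP 2.6, 3.1 and 5.2 do not say that they replace protocol section 11, and SAP 2.6 says Bonferroni will be used while 3.1 and 5.2 say Tukey. The miscount in 3.1 is resolved by its own total and by its later reference to three tests, so it is a wording slip.

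**Conclusion.** The point holds in two parts. First, 0.083 in SAP 2.6 is a misprint for 0.0083. It has no effect on N, on the stated power or on type I error under the plan as a whole. Second, the primary decision rule is not unique. The two SAP rules part over a narrow band, p from 0.0083 to about 0.0094–0.0097 at N = 24. Protocol section 11 parts from both over a wide one, up to p = 0.05, with a family-wise bound of 0.10 across the two carotenoids against 0.05 under either SAP rule.

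The power figures assume the SAP's difference and SD (4 and 4) and df = N − 6, which is inferred. The range for the Tukey level reflects df from 18 to 46.

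A conclusion that the trial lacks error control or is wrongly sized would go further than the documents allow.

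**What to change.** 1. In SAP 2.6, replace the decimal 0.083 with 0.0083 and keep 0.83%.
2. In SAP 3.1, change the count to three pairwise tests per main outcome, six in total.
3. Choose one primary multiplicity rule, state it identically in SAP 2.6, 3.1 and 5.2, and say that it supersedes the post-hoc procedure and 0.05 criterion in protocol section 11.
4. Quote power at the chosen rule, with the degrees of freedom stated. With df = N − 6, Bonferroni over six gives 96% at N = 24 and 83% at N = 18, as now printed. Tukey at 0.025 per carotenoid gives about 97% and 86%.

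The cost is SAP wording alone. Either SAP rule leaves the sample size at 24. The change should be made before the outcome data are analysed.
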